5.2. Exclusion Criteria

An individual who meets any of the following criteria will be excluded from participation in this study:

1. Body habitus that precludes patients from wearing a device on their wrist
2. Subjects without normal palpable radial artery pulse, whether congenital, due to medical intervention, or otherwise
3. Subjects with wrist circumference less than 155mm or greater than 210mm
4. Subjects implanted with VAD's or other mechanical circulatory support device whether intracorporeal or extracorporeal
5. Patients that do not have an intra-arterial blood pressure line.

5.3. Vulnerable Subjects

No vulnerable subjects will be included in this study. Given the population at the SICU, it is possible that some patients might not have capacity to consent for themselves. Each potential subject will be assessed for their capacity to provide consent. Patients who are not alert, oriented, and able to comprehend the study will not be asked to participate in this study. Only those with capacity to consent for themselves will be enrolled.

5.4. Strategies for Recruitment and Retention

Target sample size is 15 patients. The anticipated number of patients to be screened in order to reach the target enrollment is 20 patients.

Only adult patients admitted to the NYU Langone Health Surgical ICU, Cardiovascular ICU, Neurologic ICU and NYU Langone Brooklyn Surgical ICU and Neurologic ICU will be considered. Participation is voluntary and will require verbal consent. Volunteers who do not already have an intra-arterial catheter in place will not be considered.

5.4.1. Use of DataCore/Epic Information for Recruitment Purposes

Potential subjects will be identified using the daily NYU Langone Health ICU and NYU Langone Brooklyn ICU census. The study investigators have a clinical relationship with these patients and will approach them for participation.

No DataCore/Epic information will be used for recruitment.

5.5. Duration of Study Participation

The total duration of subject participation in the study is expected to be approximately 30 minutes.

5.6. Total Number of Participants and Sites

Recruitment will end when approximately 20 participants are enrolled. It is expected that approximately 20 participants will be enrolled in order to produce 15 evaluable participants.

5.7. Participant Withdrawal or Termination

5.7.1. Reasons for Withdrawal or Termination

Participants are free to withdraw from participation in the study at any time upon request. An investigator may terminate participation in the study if:

- Any clinical adverse event (AE), laboratory abnormality, or other medical condition or situation occurs such that continued participation in the study would not be in the best interest of the participant
- The participant meets an exclusion criterion (either newly developed or not previously recognized) that precludes further study participation

5.7.2. Handling of Participant Withdrawals or Termination

A subject may withdraw from the study at any time. If a subject withdraws, his or her data will not be included in this analysis. An additional subject will be needed to allow for the goal sample size to be achieved.

5.8. Premature Termination or Suspension of Study

This study may be temporarily suspended or prematurely terminated if there is sufficient reasonable cause. Written notification, documenting the reason for study suspension or termination, will be provided by the suspending or terminating party to the investigators. If the study is prematurely terminated or suspended, the PI will promptly inform the IRB and will provide the reason(s) for the termination or suspension.

Circumstances that may warrant termination or suspension include, but are not limited to:

- Determination of unexpected, significant, or unacceptable risk to participants
- Demonstration of efficacy that would warrant stopping
- Insufficient compliance to protocol requirements
- Data that are not sufficiently complete and/or evaluable
- Determination of futility

Study may resume once concerns about safety, protocol compliance, data quality are addressed and satisfy the sponsor, IRB and/or FDA.

6. Study Agent (Study drug, device, biologic, vaccine etc.) and/or Procedural Intervention

6.1. Study Agent(s) and Control Description

The device is a wristband. Because the subjects also have an intra-arterial blood pressure monitor in place, the subjects will serve as their own control.

6.1.1. Acquisition

LiveMetric will provide the blood pressure wristbands for use in this study.

6.1.2. Device Specific Considerations

The device is a wristband that will be worn by the subject for approximately 30 minutes. See the attached image for further details. The BP data will be downloaded to a laptop using Medicollector software. No patient information is included only the BP signals.

6.1.4. Administration of Intervention

The wristband device will be applied by an investigator. It will be removed by an investigator at the end of the study period.

6.1.5. Assessment of Subject Compliance with Study Intervention

The subject will be directly observed by an investigator when wearing the investigational wristband to ensure compliance.

6.2. Study Procedures/Evaluations

Blood pressure measurements from the arterial line will be recorded directly from the intra-arterial blood pressure monitor screen. Blood pressure measurements from the wristband device will be downloaded to a laptop computer using Medicollector software. No patient information will be included.

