4.1. Description of Study Design

1. A medical professional will measure simultaneous non-invasive auscultatory readings to determine the lateral difference for later adjustment of calculation accordingly. Calculation of lateral difference is provided in section (**Error! Reference source not found.**). All data from a subject shall be excluded if: i) the lateral difference of the reference systolic BP readings is more than 15 mmHg (2,00 kPa); or ii) the lateral difference of the reference diastolic BP readings is more than 10 mmHg (1,33 kPa).
2. If subject's reading is eligible, the medical professional or research personnel will place the LiveMetric wristband on the opposite limb than the one having the A-line, providing the location of the placement has intact skin.
3. During the measurement stage, BP values are simultaneously recorded from the reference invasive A-line and the LiveMetric device. In addition, other vital signs from the monitoring equipment can be collected as available (ECG, Respiratory rate, Pleth, and HR). The invasive BP values and other vital signs are captured from the Vital Signs Monitor (available in the patient's room) and the LiveMetric device. A measurement session of 30 minutes will be conducted for each subject. During the measurements, no information from the device will be provided to the investigator or study personnel. All the data will be processed and analyzed post-measurement according to the following considerations as required by the standard: only up to 10 consecutive measurements per subject will be analyzed; measurement will be made over 30 seconds of recording; consecutive meas-

urement will be considered as the next 30 seconds following at least a 60 second interval. Measurement (data points) is defined as recording or acquisition of signal from the monitor. The medical professional will take off the wristband at the end of this process.

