9.3.1. Determining the reference BP

The invasive SYS and DIA BP values shall be determined from the recordings. (The BP reading will be recorded beat to beat, without any averaging, from the A-line and from the LiveMetric device). The mean and experimental standard deviation of the SYS and DIA BP from the recordings will be determined.

Since there is no cuff inflation interruption by the LiveMetric device, the A-line ranges shall be determined from the recording for a duration of 30 seconds, while simultaneously recording the same period of the data point from the LiveMetric device.

The reference SYS is defined as the range of a ± 1 experimental standard deviation around the mean value of the invasive systolic BP values obtained during the data point range performed by the LiveMetric device. The reference DIA BP is defined as the range of ± 1 experimental standard deviation around the mean value of the invasive diastolic BP values obtained during the same period.

Isolated VPB's shall be addressed by removing the pressure pulse associated with the VPB and the following compensatory beat.

If the value obtained from the LiveMetric determination lies within the range of the reference BP as determined in (**Error! Reference source not found.**), assign an error of 0 mmHg (0 kPa) to this determination.

If the value obtained from the LiveMetric determination lies outside the range of the reference BP as determined in (**Error! Reference source not found.**) subtract the value of the determination from the adjacent limit of the range of the variation of BP. That difference represents the error for this determination.

The arithmetic mean of the error is calculated and its experimental standard deviation from the errors of each recording for each BP value (SYS & DIA) and determination for each patient.

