13.1 Data Collection and Management Responsibilities

Only anonymous data will be collected. No PHI will be retained.
Anonymous data will be recorded and saved electronically.
Intra-arterial blood pressure monitor data will be recorded automatically as per ICU standards.
Data collection will be the responsibility of the investigators and will be stored on REDCap.

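### Section 6.2 takes the A-line reference from the monitor screen, in conflict with sections 4.1, 9 and 9.3.1, which call for captured A-line data and, in 9.3.1, unaveraged beat-to-beat values

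*Combined protocol and SAP*

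**What the plan says.** The plan describes the source of the A-line values in several places.

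- **Section 6.2** (Study Procedures/Evaluations): "Blood pressure measurements from the arterial line will be recorded directly from the intra-arterial blood pressure monitor screen". The next sentence gives the other device a different route: "Blood pressure measurements from the wristband device will be downloaded to a laptop computer using Medicollector software".
- **Section 13.1** (Data Collection and Management Responsibilities): "Intra-arterial blood pressure monitor data will be recorded automatically as per ICU standards". It gives no resolution and does not mention averaging.
- **Section 4.1**: "The invasive BP values and other vital signs are captured from the Vital Signs Monitor". The same item requires the two devices to be recorded simultaneously and defines a measurement as acquiring a signal from the monitor.
- **Section 9** (opening text): data from both the A-line monitor and the wristband are to be collected and processed by validated software. A data point is usable only if the A-line range within it is below 20 mmHg systolic and 12 mmHg diastolic.
- **Section 6.1.2**: blood pressure data go to a laptop through the capture software. It is not explicit whether the A-line is included.

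The analysis rests on section 9.3.1:

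- resolution: "The BP reading will be recorded beat to beat, without any averaging, from the A-line and from the LiveMetric device"
- window: "the A-line ranges shall be determined from the recording for a duration of 30 seconds"
- reference: "The reference SYS is defined as the range of a ± 1 experimental standard deviation around the mean value", and likewise for diastolic pressure
- ectopy: "Isolated VPB's shall be addressed by removing the pressure pulse associated with the VPB and the following compensatory beat"

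**The concern.** The ±1 SD range in 9.3.1 is the yardstick for every error. A wristband value inside it scores zero; a value outside scores its distance to the nearer limit. Sections 9.3.3 and 9.3.4 then judge the device on the mean and SD of those errors. The data source therefore feeds directly into the primary endpoint.

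Section 6.2 is where site staff look for what to do, and its two adjacent sentences read as two different routes: screen for the A-line, download for the wristband. Section 9.1 asks for ten A-line values per subject at the wristband time points, so one screen number per time point would appear to satisfy both sections.

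The loss could not be repaired later. By section 12.4, data collection ends when the wristband comes off and the data are stored anonymously. Only about 15 evaluable subjects are planned.

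**Working it through.** The plan states no figure for this point, so there is none to reproduce. The check compares what 9.3.1 needs with what each route supplies, then illustrates the size.

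**1. What each step needs**

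| Step | Needs | One screen value per time point | Averaged screen values |
|---|---|---|---|
| Mean ±1 SD (9.3.1) | several unaveraged beats in 30 s | SD has divisor n − 1 = 0: undefined | computable, too narrow |
| Ectopic beat removal (9.3.1) | individual beats | not possible | not possible |
| 20/12 mmHg range check (9) | lowest and highest A-line value | not possible | range understated |

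**2. Could beats be read off a screen?** Assume a heart rate of 50–110/min. Beats per window = rate × 30/60 = 25–55. Systolic and diastolic values over ten data points = 25 × 2 × 10 = 500 to 55 × 2 × 10 = 1,100 per subject. Manual transcription is not realistic.

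**3. Effect of averaging on the range.** All inputs here are assumptions, because the documents give none: 40 beats in 30 s, sinusoidal respiratory swing ±5 mmHg at 15/min, random beat SD 2 mmHg, device error SD 8 mmHg, and a displayed value that is a moving average of 4, 8 or 12 beats.

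- Unaveraged beats: half-width ≈ √(5²/2 + 2²) = √16.5 = 4.1 mmHg.
- Share scored zero ≈ P(|Z| < 4.1/8), about 39%.
- Simulation, 40,000 windows per setting:

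| A-line values | Half-width (mmHg) | Scored zero | Error SD (mmHg) |
|---|---|---|---|
| Unaveraged beats | 4.1 | 39% | 5.2 |
| Average of 4 beats | 1.5 | 15% | 6.9 |
| Average of 12 beats | 0.6 | 6% | 7.6 |

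The 8-beat average falls between the last two rows. With a single value there is no range. If its width were set to zero, the error SD would be about 8 mmHg when the displayed value is near the window mean, and √(8² + 16.5) = 9.0 mmHg when it is one raw beat.

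**4. A different model.** With 35 independent beats, beat SD 2–6 and device SD 5–8, averaging 5–7 beats cuts the half-width from 2.0–6.0 to 0.7–2.6 mmHg and the zero share from 19–75% to 7–38%. At beat SD 4 and device SD 5 the error SD rises from 2.5 to 3.8–4.0 mmHg. The direction is the same.

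**5. Range check.** Share of windows whose unaveraged systolic range reaches 20 mmHg, under the step 3 inputs but varying the swing: 0.6% at ±5, 5.8% at ±6, 28% at ±7. None does on the averaged values. The effect is small in the base case and grows only with larger swings.

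**The case against.** The strongest reply is that 6.2 is one loose sentence in a plan that elsewhere gives the right method. Sections 4.1 and 9 provide for capture from the monitor and processing by software, 6.1.2 may do so, and 9.3.1 itself orders beat-to-beat recording from both devices. The wording of 6.2 could even be read as loose language for that capture. This much stands: the plan has a route to its reference.

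It does not dispose of the point, because 6.2 contrasts the screen with a download given only to the wristband, and nothing says which section prevails.

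Four stronger readings are tempting, and the documents do not support them:

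- *The reference cannot be built under this plan.* That holds only for a site following 6.2 literally, and only if the screen route yields single or averaged numbers. No section says what the screen shows or how it averages.
- *Section 13.1 is also incompatible.* It speaks of automatic recording to ICU standards. The resolution is unstated, not shown to be too coarse.
- *Synchronous recording is not required.* Sections 4.1 and 9.3.1 both require it. Only the method of aligning the two recordings is missing.
- *The error would flatter the device.* The narrower range does the opposite, by raising the error SD. The range-check effect is nearly absent at the ±5 mmHg swing.

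**Conclusion.** The point holds as an internal inconsistency about the source of the reference data. Section 6.2 conflicts with 4.1, 9 and 9.3.1, and 13.1 does not settle the matter. Followed literally, 6.2 gives a reference range that is undefined or too narrow. It also leaves the ectopic-beat rule and the 20/12 mmHg check unable to work as intended.

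In the illustration, the same device has an error SD of about 5.2 mmHg with beat-level data and 6.9–7.6 mmHg with averaged values. The exact sizes rest on assumed swing, beat variability, device error and display averaging. The direction of the range narrowing was the same in both models. The effect of leaving ectopic beats in was not quantified.

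This should be fixed before enrolment. It is not a fatal flaw, because the design and statistics sections already describe a workable method.

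**What to change.** Replace the A-line sentence in 6.2 with:

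> Beat-to-beat, unaveraged A-line SYS and DIA are captured electronically from the bedside monitor by the study software, time-aligned with the wristband recording, as required by 4.1, 9 and 9.3.1; screen-read or charted values are not used as the reference.

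Align 13.1 with the same source and resolution. Section 9.3.1 needs beat-level systolic and diastolic values and does not require waveform export, so no rule discarding every session without an exported waveform is needed.

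**Cost.** The change to the documents is wording, and software and a laptop are already in the plan. A 30-second data point without beat-level A-line data could not be used, so some data points or whole sessions may be lost from a study that enrols about 20 to obtain 15 evaluable. The documents do not show that the capture set-up can record both signals on aligned clocks; the site must confirm this before the first subject.

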6.2.1. Study Specific Procedures

The following information will be collected anonymously for each subject: Age, weight, current inpatient medications, general condition. No PHI will be saved.

6.2.2. Screening

Once a patient has been admitted to the NYU Langone Health Hospital, Surgical ICU, Cardiovascular ICU, or Neurologic ICU or NYU Langone Brooklyn Surgical ICU or Neurologic ICU, and an intra-arterial blood pressure monitor has been placed, an investigator will approach the subject to determine willingness to participate in the study and to obtain verbal consent.

7. Assessment of Safety

7.1. Specification of Safety Parameters

No specific safety parameters. The only anticipated risk is the potential discomfort associated with wearing the wristband device.

7.1.1. Definition of Adverse Events (AE)

An **adverse event** (AE) is any symptom, sign, illness or experience that develops or worsens in severity during the course of the study. Intercurrent illnesses or injuries should be regarded as adverse events. Abnormal results of diagnostic procedures are considered to be adverse events if the abnormality:

- results in study withdrawal
- is associated with a serious adverse event
- is associated with clinical signs or symptoms
- leads to additional treatment or to further diagnostic tests
- is considered by the investigator to be of clinical significance

7.1.2. Definition of Serious Adverse Events (SAE)

Serious Adverse Event

Adverse events are classified as serious or non-serious. A **serious adverse event** is any AE that is:

- fatal
- life-threatening
- requires or prolongs hospital stay
- results in persistent or significant disability or incapacity
- a congenital anomaly or birth defect
- an important medical event

Important medical events are those that may not be immediately life threatening, but are clearly of major clinical significance. They may jeopardize the subject, and may require intervention to prevent one of the other serious outcomes noted above. For example, drug overdose or abuse, a seizure that did not result in in-patient hospitalization, or intensive treatment of bronchospasm in an emergency department would typically be considered serious.

All adverse events that do not meet any of the criteria for serious should be regarded as **non-serious adverse events**.

7.1.3. Definition of Unanticipated Problems (UP)

Unanticipated Problems Involving Risk to Subjects or Others

Any incident, experience, or outcome that meets all of the following criteria:

- Unexpected in nature, severity, or frequency (i.e. not described in study-related documents such as the IRB-approved protocol or consent form, the investigators brochure, etc)

- Related or possibly related to participation in the research (i.e. possibly related means there is a reasonable possibility that the incident experience, or outcome may have been caused by the procedures involved in the research)
- Suggests that the research places subjects or others at greater risk of harm (including physical, psychological, economic, or social harm).

This definition could include an unanticipated adverse device effect, any serious adverse effect on health or safety or any life-threatening problem or death caused by, or associated with, a device, if that effect, problem, or death was not previously identified in nature, severity, or degree of incidence in the investigational plan or application (including a supplementary plan or application), or any other unanticipated serious problem associated with a device that relates to the rights, safety, or welfare of subjects (21 CFR 812.3(s)).

7.2. Classification of an Adverse Event

7.2.1. Severity of Event

For AEs not included in the protocol defined grading system, the following guidelines will be used to describe severity.

- **Mild** – Events require minimal or no treatment and do not interfere with the participant’s daily activities.
- **Moderate** – Events result in a low level of inconvenience or concern with the therapeutic measures. Moderate events may cause some interference with functioning.
- **Severe** – Events interrupt a participant’s usual daily activity and may require systemic drug therapy or other treatment. Severe events are usually potentially life-threatening or incapacitating.

7.2.2. Relationship to Study Agent

The clinician’s assessment of an AE’s relationship to study agent (drug, biologic, device) is part of the documentation process, but it is not a factor in determining what is or is not reported in the study. If there is any doubt as to whether a clinical observation is an AE, the event should be reported. All AEs must have their relationship to study agent assessed. In a clinical trial, the study product must always be suspect. To help assess, the following guidelines are used.

- **Related** – *The AE is known to occur with the study agent, there is a reasonable possibility that the study agent caused the AE, or there is a temporal relationship between the study agent and event. Reasonable possibility means that there is evidence to suggest a causal relationship between the study agent and the AE.*
- **Not Related** – *There is not a reasonable possibility that the administration of the study agent caused the event, there is no temporal relationship between the study agent and event onset, or an alternate etiology has been established.*

7.2.3. Expectedness

The only expected potential risk is the possible discomfort associated with wearing the wristband. No other adverse events are expected.

7.3. Time Period and Frequency for Event Assessment and Follow-Up

The occurrence of an AE or SAE may come to the attention of study personnel during study visits and interviews of a study participant presenting for medical care, or upon review by a study monitor. All AEs including local and systemic reactions not meeting the criteria for SAEs will be captured on the appropriate RF. Information to be collected includes event description, time of onset, clinician's assessment of severity, relationship to study product (assessed only by those with the training and authority to make a diagnosis), and time of resolution/stabilization of the event. All AEs occurring while on study must be documented appropriately regardless of relationship. All AEs will be followed to adequate resolution.

Any medical condition that is present at the time that the participant is screened will be considered as baseline and not reported as an AE. However, if the study participant's condition deteriorates at any time during the study, it will be recorded as an AE. UPs will be recorded in the data collection system throughout the study.

Changes in the severity of an AE will be documented to allow an assessment of the duration of the event at each level of severity to be performed. AEs characterized as intermittent require documentation of onset and duration of each episode.

The PI will record all reportable events with start dates occurring any time after informed consent is obtained until 7 (for non-serious AEs) or 30 days (for SAEs) after the last day of study participation. At each study visit, the investigator will inquire about the occurrence of AE/SAEs since the last visit. Events will be followed for outcome information until resolution or stabilization.

All unresolved adverse events should be followed by the investigator until the events are resolved, the subject is lost to follow-up, or the adverse event is otherwise explained. At the last scheduled visit, the investigator should instruct each subject to report any subsequent event(s) that the subject, or the subject's personal physician, believes might reasonably be related to participation in this study. The investigator should notify the study sponsor of any death or adverse event occurring at any time after a subject has discontinued or terminated study participation that may reasonably be related to this study. The sponsor should also be notified if the investigator should become aware of the development of cancer or of a congenital anomaly in a subsequently conceived offspring of a subject that has participated in this study.

